5.4.2.4.6. Study Intervention Completion at Week 48 and During Follow-up

Participants will complete treatment with JNJ-3989 after a fixed duration of 48 weeks. If all of the below criteria are met based on clinical laboratory tests performed at Week 44, treatment with NA will also be completed at the next scheduled visit (ie, Week 48):

- The participant has ALT <3x ULN, AND
- The participant has HBV DNA <LLOQ, AND
- The participant is HBeAg negative, AND
- The participant has HBsAg <10 IU/mL.

Participants who do not meet the above criteria at Week 48 should continue NA treatment during the 48-week follow-up phase. Participants who are receiving optional treatment with PegIFN- α 2a and who have not met NA treatment completion criteria at Week 48 may have NA treatment completion criteria assessed at the end of treatment with PegIFN- α 2a and stop NA if criteria are met.

Proportion of participants who have met NA completion criteria, and reasons for not meeting, will be summarized at Week 48 and at the end of treatment with PegIFN- α 2a.

5.4.2.4.7. NA Re-Treatment During Follow-up

Proportion of participants who have NA re-treatment during follow-up will be summarized.

5.4.2.4.8. ALT Normalization after NA Re-Treatment

Proportion of participants who have ALT \geq ULN before NA re-treatment and reach ALT normalization after NA re-treatment during follow-up will be summarized.

5.4.2.4.9. Thresholds On Multiple Markers

The number and proportion of participants who meet the following blood marker reduction/seroclearance thresholds at 12, 24, 36 and 48 weeks, respectively, after stopping all study interventions (including NA and PegIFN- α 2a) and not having NA re-treated will be summarized descriptively for each marker and each threshold listed below.

- **HBsAg<LLOQ and HBV DNA**
 - HBsAg<LLOQ and HBV DNA<LLOQ**
 - HBsAg<LLOQ and HBV DNA≥LLOQ
 - HBsAG<LLOQ and HBV<2,000 IU/ml
- **HBsAg≥LLOQ and HBV DNA<2,000 IU/ml**
 - HBsAg≥LLOQ and HBV DNA<LLOQ**
 - HBsAg≥LLOQ and HBV DNA≥LLOQ
 - HBsAg≥LLOQ and LLOQ ≤HBV DNA<2,000 IU/ml
- **HBsAg≥LLOQ and HBV DNA≥2,000 IU/ml**
 - HBsAg<100 IU/mL and HBV DNA≥2,000 IU/ml
 - HBsAg≥100 IU/mL and HBV DNA≥2,000 IU/ml
- **HBsAg<100 IU/ml and HBV DNA<2000 IU/ml**
- **HBsAg<100 IU/ml and HBV DNA<LLOQ****

** HBV DNA<LLOQ will be summarized overall. Additional analyses may assess HBV DNA<LLOQ TD versus TND.

Due to the exploratory objectives of this study, additional blood marker reduction/seroclearance thresholds may be added at a later point in time according to the clinical interest.

5.4.2.5. Functional Cure

A participant will be defined as having achieved Functional Cure (FC) at a given time point during the FU phase if he/she has HBsAg seroclearance (as defined in Section 5.4.2.1) at that time point and has stopped all study interventions (including NA and PegIFN- α 2a) for at least 24 weeks without re-treatment.

Participants who discontinue treatment prior to Week 48 (except for JNJ-6379), or who withdraw from the study prior to the given time point, will be considered as non-responders for FC in this study. The CRF pages of ‘Treatment Disposition of JNJ-3989’, ‘Treatment Disposition of NA Treatment’, ‘Treatment Disposition for NA Re-Treatment’ and ‘Treatment Disposition for PegIFN-alpha2a’ will be checked to ensure all treatment actually stopped.

Subjects still in the study at a given time point but with missing HBsAg assessment at that time after implementation of LOCF (as described in Section 5.4.2.1), will be considered as non-responders.

Number and proportion of participants achieving FC will be summarized at 24, 36, and 48 weeks after stopping all study interventions (including NA and PegIFN- α 2a). Subjects who never reach such time points will be considered as non-responders.

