Leukapheresis (optional) v									(X)							

Phase			Follow-up a,b														
			+/- FU W24 d							Optional Biopsy	Post biopsy Visit	FU W28	FU W32	FU W36	FU W40	FU W44	
Follow up (FU) Week (W)	FU W2	FU W4	FU W8	FU W12	FU W16	FU W20	FU W24										Extended FU to maximum FU W72 y
FU Study Day (Window)	15 (+/ 4d)	29 (+/ 4d)	57 (+/ 4d)	85 (+/ 4d)	113 (+/ 4d)	141 (+/ 4d)	169 (+/ 4d)	169 (+/ 4w)	≥1w ≤3w After Biopsy	197 (+/ 4d)	225 (+/ 4d)	253 (+/ 4d)	281 (+/ 4d)	309 (+/ 4d)	337 (+/ 4d)	maximum 505 (+/ 4d)	
Visits in case all treatments including NA stopped	X	X	X	X	X	X	X			X	X	X	X	X	X	X	
Visits in case NA is not stopped	X	X	(X) c	X	(X) c	(X) c	X			(X) c	(X) c	X	(X) c	(X) c	X	X	
Immune cells (PBMCs) w	X			X			X										
Pharmacogenomics (Host DNA)																	
Epigenetic research	X			X			X									X	
Ongoing Participant Review																	
Concomitant therapy x	X	X	X	X	X	X	X	X	X	X	X	X	X	X	X	X	
Adverse events x	X	X	X	X	X	X	X	X	X	X	X	X	X	X	X	X	

ALP: alkaline phosphatase; ALT: alanine aminotransferase; AST: aspartate aminotransferase; d: days; DBP: diastolic blood pressure; DNA: deoxyribonucleic acid; ECG: electrocardiogram; eGFR: estimated glomerular filtration rate; EOS: end of study; FU: follow-up; HBcrAg: hepatitis B core-related antigen; HBe(Ag): hepatitis B e (antigen); HBs(Ag): hepatitis B surface (antigen); HBV: hepatitis B virus; HCC: hepatocellular carcinoma; ICF: informed consent form; NA: nucleos(t)ide analog; PBMC: peripheral blood mononuclear cells; RNA: ribonucleic acid; SBP: systolic blood pressure; ULN: upper limit of normal; W: Week.

- All follow-up study visits are to be scheduled relative to the last dose of JNJ-3989. An unscheduled visit can be performed upon the investigator's discretion, in case of HBV DNA elevations, ALT elevations, other signs of worsening of liver disease, or for any other reason during follow-up.
- Participants who withdraw consent during follow-up will be offered an optional safety follow-up visit.
- Visit is optional for participants who continue NA treatment and for participants who have restarted NA treatment during the follow-up period, provided that their HBV DNA and ALT values are stable.

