1.2. Study Design

A target of 24 chronic HBV-infected male and female participants, 18-65 years (inclusive) of age

will be enrolled in Panels 1 and 2, approximately 12 participants in each panel. In Panel 3, a target of 4-6 chronic HBV-infected male and female participants will be enrolled.

- Panel 1 will consist of participants who are HBeAg positive and not currently treated.
- Panel 2 will consist of participants who are HBeAg negative and virologically suppressed by ETV, TD, or TAF treatment.
- Panel 3 will consist of participants who are HBeAg positive or negative and are either not currently treated or virologically suppressed by ETV or TD treatment.

The study will be conducted in 3 phases for all participants:

- A **screening phase** (4 to 6 weeks),
- An **open-label study intervention phase** (48 weeks),
- A **follow-up phase** (48 weeks). Note that the follow-up period will be extended up to an additional 24 weeks for participants who are receiving optional treatment with PegIFN- α 2a and who meet NA treatment completion criteria at the end of treatment with NA and PegIFN- α 2a to ensure all participants have at least one year of follow-up after NA treatment cessation.

The duration of individual participation will be up to 102 weeks for participants who stop NA treatment at the end of the open-label phase, or up to 126 weeks for participants who stop NA treatment during the follow-up phase.

Prior to Protocol Amendment 5, in Panels 1 and 2, participants were randomized in a 1:1 ratio within each panel to receive one of the following interventions (i.e., treatments) for 48 weeks:

- **Arm 1**, combination regimen JNJ-3989+JNJ-6379+NA:
 - 200 mg JNJ-3989 (SC injection Q4W, with the last injection at Week 44), and
 - 250 mg JNJ-6379 (tablets qd), and
 - NA: ETV, TD, or TAF (tablets qd)
- **Arm 2**, combination regimen JNJ-3989+NA:
 - 200 mg JNJ-3989 (SC injection Q4W, with the last injection at Week 44), and
 - NA: ETV, TD, or TAF (tablets qd).

As of Protocol Amendment 5, in Panels 1 and 2, participants who were previously randomized to Arm 1 had to stop JNJ-6379 treatment immediately but will still receive JNJ-3989 and NA – effectively joining Arm 2. New participants will enroll without randomization to Arm 2.

No participants were enrolled in Panel 3 before Protocol Amendment 5 was in effect. Therefore, all Panel 3 participants will enroll without randomization to receive the Arm 2 regimen.

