5.1.2. Visit Windows

As participants do not always adhere to the protocol visit schedule, visits will be allocated within each phase to an analysis time point based on the time intervals in [Table 2](#).

If a participant has two or more actual visits in a visit window (“time interval” in [Table 2](#)), only one will be selected as the protocol visit according to the following rules:

1. The measurement closest to the target day will be used.
2. If the measurements fall equidistant from the target day, the last measurement in chronological order will be used.
3. If there are two or more measurements on the same day, then the last measurement in chronological order will be used. If the time of the assessment is not available, the highest record/sequence number will be selected.

Only the protocol visits will be included for calculating summary statistics across participants within a time point or for statistical models using longitudinal data. However, listings or figures

of individual participant-level data (including spaghetti plots), or analyses that identify a maximum or minimum value across time points (e.g., maximum ALT value), may include all measurements.

End of treatment (i.e., EOT) and end of study (i.e., EOS) time points will be included in all analysis over time unless stated otherwise.

Special rule for Follow-up Week 48 (FU W48): Note that the time interval for FU W48 is open on the right, $[324, +\infty)$, while the next time interval is $[352, 379]$. Any visit in follow-up days $[324, 351]$ will be assigned to FU W48. If a patient does not have a visit date in that interval but does have visits on or after follow-up day 352, then the earliest such visit will be assigned to FU W48. Any additional visits on or after follow-up day 352 will be assigned to an “Ext” follow-up visit according to [Table 2](#).

Table 2: Visit Windows

a) Screening and Open-Label Phases

Analysis phase	Target day	Analysis time point (Week)	Analysis time point (Label)	Open-label time interval (Days)
Screening	$-\infty$	-1	Screening	<0
Open-Label	1	0	Baseline	Pre-dose: 1
	15	2	Week 2	$[2, 22]$
	29	4	Week 4	$[23, 43]$
	57	8	Week 8	$[44, 71]$
	85	12	Week 12	$[72, 99]$
	113	16	Week 16	$[100, 127]$
	141	20	Week 20	$[128, 155]$
	169	24	Week 24	$[156, 183]$
	197	28	Week 28	$[184, 211]$
	225	32	Week 32	$[212, 239]$
	253	36	Week 36	$[240, 267]$
	281	40	Week 40	$[268, 295]$
	309	44	Week 44	$[296, 323]$
	337	48	Week 48	$[324, 351]$

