	last visit in open-label phase	49 ^a	EOT ^a	

^a End of treatment (EOT) visit will be the last post-baseline visit in open-label phase as defined in [Table 1](#).

b) Follow-Up Phase

Analysis phase	Target day	Analysis time point (Week)	Analysis time point (Label)	Follow-up time interval (Days)
Follow-up	15	50	Follow-up Week 2	[1, 22]
	29	52	Follow-up Week 4	[23, 43]
	57	56	Follow-up Week 8	[44, 71]
	85	60	Follow-up Week 12	[72, 99]
	113	64	Follow-up Week 16	[100, 127]
	141	68	Follow-up Week 20	[128, 155]
	169	72	Follow-up Week 24	[156, 183]
	197	76	Follow-up Week 28	[184, 211]
	225	80	Follow-up Week 32	[212, 239]
	253	84	Follow-up Week 36	[240, 267]
	281	88	Follow-up Week 40	[268, 295]
	309	92	Follow-up Week 44	[296, 323]
	337	96	Follow-up Week 48	[324, $+\infty$)
	365	100	Follow-up Week 52 (Ext)	[352, 379]
	393	104	Follow-up Week 56 (Ext)	[380, 407]
	421	108	Follow-up Week 60 (Ext)	[408, 435]
	449	112	Follow-up Week 64 (Ext)	[436, 463]
	477	116	Follow-up Week 68 (Ext)	[464, 491]
	505	120	Follow-up Week 72 (Ext)	[492, $+\infty$)
	last visit in the study	999 ^a	EOS ^a	

^a End of study (EOS) visit (last available data during the follow-up phase) will be the last visit in the study.

Note: The visits labeled with “Ext” are only for participants who completed PegIFN administration and NA treatment during the follow-up phase.

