5.4.2. Blood Peripheral Secondary Endpoints

5.4.2.1. HBsAg Seroclearance

HBsAg seroclearance, defined as quantitative HBsAg <LLOQ (see Table 3), will be evaluated at all time points.

If the HBsAg value at Weeks 40 or 48 is missing, the LOCF approach will be used with the condition that no value more than 8 weeks prior to the respective time point may be carried forward. At FU Weeks 12, 24, 36 and 48, and at 24, 36, and 48 weeks after stopping all study

interventions, if an HBsAg value is missing, then LOCF approach will be used with the condition that no value more than 12 weeks prior to the respective time point will be used. For all other time points, seroclearance will be analyzed as observed case without imputation.

The proportion of participants who achieve HBsAg seroclearance over time will be summarized.

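### Functional cure 48 weeks off treatment is a failure by schedule for participants who stop NA at Week 48 and complete a 24-week PegIFN course; two further cells depend on an unstated LOCF precedence

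*SAP*

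**What the plan says.** SAP 5.4.2.5 defines functional cure as HBsAg seroclearance with all interventions, including NA and PegIFN, stopped for at least 24 weeks without re-treatment. It reports the rate at 24, 36 and 48 weeks after the last intervention stops, and closes with: "Subjects who never reach such time points will be considered as non-responders".

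LOCF appears in two places. SAP 5.4.2.1 allows it at 24, 36 and 48 weeks after stopping all interventions, provided that "no value more than 12 weeks prior to the respective time point will be used". SAP 5.4.2.5 takes up that rule for "Subjects still in the study at a given time point but with missing HBsAg assessment at that time after implementation of LOCF" and counts those participants as non-responders.

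PegIFN starts after the Week 40 biopsy and before the Week 48 visit, and lasts 12 or 24 weeks (SAP 1.2). If the Week 44 laboratory criteria are met, "treatment with NA will also be completed at the next scheduled visit", that is, Week 48 (SAP 5.4.2.4.6). SAP 1.2 sets participation at "up to 102 weeks for participants who stop NA treatment at the end of the open-label phase". The note to SAP Table 2 says that the extension visits are "only for participants who completed PegIFN administration and NA treatment during the follow-up phase". Protocol Sections 4.4 and 8 tie the extension to one year after NA cessation, not after PegIFN cessation.

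**The concern.** For most participants, counting an unreached time point as a failure deals with dropouts and with people who never stop NA. In one group it does something else. A PegIFN participant who qualifies to stop NA at Week 48 can complete every planned visit, be HBsAg negative at the last one, and still be scored a failure because no visit was planned late enough.

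The effect is uneven within PegIFN. Participants who qualify to stop NA later, at the end of PegIFN, may be followed to Follow-up Week 72 and can be counted as cured at 48 weeks. Those who qualified earlier may not be. A fall from the 24-week to the 48-week rate could then be read as loss of cure when part of it is the visit calendar.

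**Working it through.** **Plan's own figures.** Longest screening 6 + intervention 48 + follow-up 48 = 102 weeks; 102 + 24 = 126 weeks. Both match SAP 1.2. Follow-up Week 48 is study Week 48 + 48 = 96, and Follow-up Week 72 is study Week 120 (SAP Table 2).

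**Weeks off all treatment at the last planned visit.** NA stops at Week 48 and PegIFN starts at week s, nominally 40 to 48. With the stop taken as the end of the course:

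- 12-week course: 96 - (s + 12) = 84 - s, which is 36 to 44 weeks.
- 24-week course: 96 - (s + 24) = 72 - s, which is 24 to 32 weeks.

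Other stop dates shift these slightly. Counting from the last weekly injection adds one week (37-45 and 25-33). The SAP 5.1.3 rule, last injection plus 10 days, gives 35.6-43.6 and 23.6-31.6.

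**Against the time points, with the LOCF gap from Week 96 (course-end convention).**

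| Course | Time point | Weeks off at Week 96 | LOCF gap (limit 12) | Result |
|---|---|---|---|---|
| 12-week | 36 | 36-44 | none | reached |
| 12-week | 48 | 36-44 | 4-12 | depends on precedence |
| 24-week | 24 | 24-32 | none | reached |
| 24-week | 36 | 24-32 | 4-12 | depends on precedence |
| 24-week | 48 | 24-32 | 16-24 | fails either way |

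**Visit margin.** SAP Table 2 opens the Follow-up Week 48 window at day 324 for target day 337, a margin of 13 days or 1.86 weeks. The Follow-up Week 36 window has the same margin (253 - 240 = 13). With it, 48 weeks counts as reached from 48 - 1.86 = 46.1 weeks, and 36 weeks from 34.1. The best nominal values, 45 weeks for the 12-week course at 48 and 33 weeks for the 24-week course at 36, still fall short. The lowest 24-week value, 23.6, is above 24 - 1.86 = 22.1. Non-PegIFN participants have 96 - 48 = 48 weeks and are unaffected.

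**Edge of the biopsy window.** The Week 40 biopsy may fall 4 weeks either side (Protocol 1.3.1). A start at Week 36 gives 84 - 36 = 48 weeks (12-week course) or 72 - 36 = 36 weeks (24-week course). With the 13-day margin, the latest start at which the 12-week course reaches 48 weeks, or the 24-week course reaches 36, is about Week 37.4 (5.1.3 rule), 37.9 (course end) or 38.9 (last injection). Class membership there depends on the convention. At a Week 36 start the 24-week course has a gap of 48 - 36 = 12 weeks, which LOCF could just fill.

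**Comparison group.** PegIFN participants who stop NA with PegIFN stop at Weeks 52-72. Their 48-week point falls at Weeks 100-120, within Follow-up Week 72.

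**Follow-up anchor.** Protocol 1.3.2 states: "All follow-up study visits are to be scheduled relative to the last dose of JNJ-3989". That dose is at Week 44, so Follow-up Week 48 would be Week 92. The values become 32-40 weeks (12-week course), 20-28 weeks (24-week course) and 44 weeks without PegIFN. SAP Table 2 counts from Week 48.

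**The case against.** The best defence is that SAP 5.4.2.5 takes its definition of seroclearance from 5.4.2.1, and 5.4.2.1 names the 36- and 48-week off-treatment points for LOCF. Two of the three shortfall cells could then be filled. This stands as a possible reading. The other is equally open, since 5.4.2.5 mentions LOCF only for subjects still in the study and then fails those who never reach the point. Neither reading fills the completed 24-week course at 48 weeks from a nominal start.

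Not every course is completed. Protocol 7.1 lists many reasons to stop PegIFN at once. A 24-week course started at Week 42 and stopped after 10 weeks ends at Week 52, leaving 96 - 52 = 44 weeks, so 36 weeks is reached. The point is therefore limited to completed courses.

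No protocol-defined endpoint is harmed. The protocol defines functional cure at 24 weeks after end of treatment, SAP 5.5.2 models it at Off-Treatment Week 24, and there is no formal testing. Failing unreached time points is conservative and openly stated. SAP 5.1.6 plans some analyses by PegIFN use and duration, and the HBsAg spaghetti plots show individual courses. All this lowers the stakes. It does not make the 36- and 48-week rows readable: functional cure is not named in the PegIFN split, and no table counts participants without a planned visit.

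**Conclusion.** The point holds in a limited form. With NA stopped at Week 48, follow-up counted from Week 48 and a full 24-week PegIFN course started at Weeks 40-48, failure at 48 weeks off treatment follows from the schedule under either LOCF reading. Failure of the 12-week course at 48 weeks and of the 24-week course at 36 weeks follows only if the last sentence of 5.4.2.5 prevails. Participants who stop PegIFN early, or start at about Weeks 36-38, may escape.

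A reader might infer that all three cells fail regardless. The 12-week LOCF in 5.4.2.1 prevents that conclusion. A reader might also infer that the 24-week functional-cure rate is distorted; it is not, if follow-up runs from Week 48. Nor do the documents support a claim of net bias against PegIFN in a yes/no comparison: PegIFN is optional and not randomised, and the net effect is unknown.

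The number affected is unknown and may be zero. PegIFN uptake, course length and the Week 48 NA-completion count are not given, and the SAP Figure 2 note allows NA to stop later in PegIFN participants. As an assumption only, the 19.1% meeting the NA criteria at Week 48 in the JNJ-3989 200 mg arm of the Phase 2b study (Protocol Appendix 10) would be 0.191 x 24 = 4.6 participants, before requiring PegIFN use and seroclearance. If 0, 1, 2 or 3 cures were missed, the overall rate would fall by 0, 4.2, 8.3 or 12.5 points of 24; one cure is 8.3 points of a 12-participant panel.

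**What to change.** In SAP 5.4.2.5:

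1. State whether the 5.4.2.1 LOCF applies to participants whose planned follow-up ends before the time point.
2. At 36 and 48 weeks, add a row for participants who stopped all treatment without re-treatment but whose scheduled last visit falls before the time point. Define it from stop dates and the visit schedule only, never from HBsAg, because interim data have already been seen. Use one stated stop-date convention and the 13-day margin of Table 2. Give their last HBsAg status.
3. Show the rate with these participants excluded beside the current all-failures rate, with neither standing alone.
4. Use the same denominators in 5.4.2.4.9, and base any PegIFN yes/no contrast of functional cure on 24 weeks off treatment.

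The follow-up anchors in Protocol 1.3.2 (last JNJ-3989 dose) and SAP Table 2 (Week 48) must be reconciled, since the classes and the 24-week rate depend on them.

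The cost is SAP wording and one extra row per table, from dates already collected. The downside is a smaller, selected denominator in the second rate, which is why the class count and the all-failures rate must appear with it.

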5.4.2.6. Flares

5.4.2.6.1. Definition

The criteria based on blood markers/lab tests for each of the flare types are defined as below.

1. **Virologic flare** is defined as follows:

Derivation 1. This derivation of virologic flare will be assessed only for those participants who are off-treatment and had $\text{HBV DNA} < \text{LLOQ}$ at the last observed point on-treatment.

The start date of a confirmed virologic flare is defined as the first date of two consecutive visits with $\text{HBV DNA} > 200 \text{ IU/mL}$. The end date of the same confirmed virologic flare is defined as the first date when HBV DNA value returns to $\leq 200 \text{ IU/mL}$ or the date of NA treatment restart, whichever comes first. Each virologic flare will be categorized based on the confirmed (i.e., two consecutive values) peak HBV DNA above any of the three thresholds within the start and end date of that flare as follows: 20,000 IU/mL , 2,000 IU/mL , and 200 IU/mL .

- 1 (Yes) = confirmed** $\text{HBV DNA} >$ peak threshold.
- 0 (No) = at least one off-treatment HBV DNA measurement available and not meeting the criteria of confirmed $\text{HBV DNA} >$ peak threshold.
- 2 (Not applicable) = no off-treatment HBV DNA quantitative measurements available.

Derivation 2. This derivation of virologic flare will be assessed only for those participants who are off-treatment and had $\text{HBV DNA} \geq \text{LLOQ}$ at the last observed point on-treatment.

The start date of a confirmed virologic flare is defined as the first date of two consecutive visits with HBV DNA log_{10} increase $> 1 \log_{10}$ from EOT. The end date of the same confirmed virologic flare is defined as the first date when HBV DNA log_{10} increase from end of treatment returns to $\leq 1 \log_{10}$ or the date of NA treatment restart, whichever comes first. Each virologic flare will be categorized based on the confirmed (i.e., two consecutive values) peak HBV DNA increase above any of the three thresholds within the start and end date of that flare as follows: $1 \log_{10}$, $2 \log_{10}$, $3 \log_{10}$.

- 1 (Yes) = confirmed** HBV DNA increase from EOT $>$ peak threshold
- 0 (No) = at least one off-treatment HBV DNA measurement available and not meeting the criteria of confirmed HBV DNA increase from EOT $>$ peak threshold.
- 2 (Not applicable) = no off-treatment HBV DNA quantitative measurements available.

** Confirmed means that the criterion should be fulfilled at 2 or more consecutive time points or at the last observed time point.

2. **Off-treatment biochemical flare** is defined as follows:

The start date of a confirmed off-treatment biochemical flare is defined as the first date of two consecutive visits with ALT and/or AST $\geq 3 \times \text{ULN}$ and $\geq 3 \times \text{nadir}$ (i.e., lowest value observed up

to the start of the flare) while the participant does not receive any of the study interventions. The end date of the same off-treatment biochemical flare is defined as the first date when there is a 50% reduction from the peak ALT and/or AST level and <3 x ULN.

- 1 (Yes) = confirmed^{**} ALT and/or AST ≥ 3 x ULN and ≥ 3 x nadir (i.e., lowest value observed up to the start of the flare)
- 0 (No) = otherwise

3. On-treatment biochemical flare is defined as follows:

The start date of a confirmed on-treatment biochemical flare is defined as the first date of two consecutive visits with ALT and/or AST ≥ 3 x ULN and ≥ 3 x nadir (i.e., lowest value observed up to the start of the flare) while the participant receives any of the study interventions. The end date of the same on-treatment biochemical flare is defined as the first date when there is a 50% reduction from the peak ALT and/or AST level and <3 x ULN, regardless of stopping study interventions.

- 1 (Yes) = confirmed^{**} ALT and/or AST ≥ 3 x ULN and ≥ 3 x nadir (i.e., lowest value observed up to the start of the flare)
- 0 (No) = otherwise

4. Clinical flare is defined as follows:

A clinical flare occurs either when a virologic flare and biochemical flare overlap in time or when a biochemical flare starts within 4 weeks following the end of a virologic flare.

The start date of a clinical flare is defined as the minimum start date of the virologic flare and biochemical flare. The end date of a clinical flare is defined as the maximum end date of the virologic flare and biochemical flare, i.e., the later date between HBV DNA returns to ≤ 200 IU/mL (or ≤ 1 log₁₀) and 50% reduction from the peak ALT and/or AST level and <3 x ULN reached during the biochemical flare.

- 1 (Yes) = confirmed^{**} HBV DNA $>$ peak threshold (for derivation 1 of virologic flare) or HBV DNA increase from end of treatment $>$ peak threshold (for derivation 2 of virologic flare) and confirmed^{**} ALT and/or AST ≥ 3 x ULN and ≥ 3 x nadir (i.e., lowest value observed up to the start of the biochemical flare).
- 0 (No) = otherwise

^{**} Confirmed means that the criterion should be fulfilled at 2 or more consecutive time points or at the last observed time point.

The virologic and clinical flares will be assessed only off-treatment, while biochemical flares will be identified on-treatment and off-treatment, respectively. On-treatment virologic flares are described as virologic HBV breakthrough in Section 5.4.2.7.

On-treatment will be defined as the time periods in which the participant receives any of the study interventions (JNJ-3989 or JNJ-6379 or NA or PegIFN- α 2a). Off-treatment will be defined as the

periods when the participants do not receive any of the study interventions (JNJ-3989, JNJ-6379, NA, and PegIFN- α 2a).

The incidence rate will be calculated and summarized for each type of on-treatment or off-treatment flares (virologic, biochemical and clinical) separately, as well as the overall incidence of participants experiencing at least one flare, regardless of type. Additionally, for each participant the total number of flares the participant experienced will be counted by type. Such counts will be used to summarize the distribution of the total number of flares by type and by study panel.

For on-treatment biochemical flares, the incidence of flares causing treatment discontinuation will be summarized. Further, for off-treatment flares, the count and percentage of participants who experienced a flare followed by NA re-treatment will be summarized by flare type. Similarly, the incidence of flares followed by the achievement of HBsAg seroclearance (at any time) will be summarized by flare type.

Flares that are associated with signs of liver decompensation will be provided in a listing.

